### **7.4.2 Deterioration in Renal Function**

Serum creatinine and eGFR utilizing the CKD-EPI formula, as reported by the central laboratory, will be used for the assessment of renal function at every visit including unscheduled visits.

It is recognized that eGFR may be unreliable at higher values ( $>100$  mL/min/1.73 m^2). FSGS subjects with nephrotic-range proteinuria frequently have wide fluctuations in serum creatinine (and therefore eGFR) which are not representative of true renal dysfunction. Chronic kidney disease is defined as eGFR  $<60$  mL/min/1.73 m^2 for  $\geq 3$  months [28], with or without kidney damage.

#### **7.4.2.1 Decrease in eGFR $>30\%$ and eGFR $<90$ mL/min/1.73 m^2**

During the treatment period, any subject experiencing a  $>30\%$  decrease in eGFR from baseline (baseline eGFR is defined as the last assessment prior to first dose of study treatment) to  $<90$  mL/min/1.73 m^2 will have study treatment interrupted until a repeat test can be performed (unscheduled visit to be completed within 48 hours). If the decrease is confirmed at the

unscheduled visit and not due to potential contributing factors (e.g., high baseline eGFR, the addition or modification of non-steroidal anti-inflammatory drugs (NSAIDs), ACEIs, ARBs, a concurrent state of dehydration, overdosing with study treatment, renal flare, etc.), the case should be discussed with the Medical Monitor, the study treatment should continue to be withheld, and eGFR retested within 48 hours. (Note: doses of ACEIs, ARBs, diuretics, and/or lipid lowering therapy are to remain stable throughout the study.) If the eGFR decrease is not confirmed, the study treatment can be restarted at 2 capsules BID and increased as tolerated with discussion with the Medical Monitor.

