### **5.2 Inclusion Criteria**

The following inclusion criteria must be met for each subject:

1. Written informed consent before any study-specific procedures are performed.
2. Male or female subjects with a minimum age of 18 years (or legal age of consent if >18 years) to 75 years of age, inclusive, at the time of consent.
3. Primary FSGS diagnosed by renal biopsy within 6 months prior to the screening visit. Biopsy results over 6 months prior to screening may be permitted following review with the Medical Monitor to confirm eligibility (see [Appendix 3](#)).
4. At initial screening assessment and at last qualifying assessment during screening period prior to baseline, FSGS subjects must have a urine protein creatinine ratio (UPCR) of  $\geq 2.0$  mg/mg. Subjects can be treatment-naïve or receiving steroid treatment (oral or intravenous (IV)) for FSGS. Subjects taking steroids must show signs of improvement in proteinuria, defined as at least a 20% improvement in UPCR from initiation of steroids to the last stability assessment prior to baseline. Subjects who have discontinued steroid treatment due to poor tolerability may be considered for the study. Subjects should also have a serum albumin level of  $\leq 3.2$  g/dL at screening and at the last qualifying assessment prior to baseline; subjects with serum albumin  $> 3.2$  g/dL may be included following review to confirm primary FSGS and after discussion with the Medical Monitor.
5. All subjects should be treated with ACEIs and/or ARBs unless they have documented intolerance or contraindication to these medications. Doses of these agents must be stable for at least 2 weeks prior to baseline, with BP  $\leq 150/90$  mmHg at the baseline visit (Visit 2).
  - a) Subjects with nephrotic edema may be treated with diuretics during the screening period. Volume status should be optimized based on the clinical judgment of the Investigator and the doses of diuretics must be stable in the 2 weeks prior to baseline.
  - b) At the discretion of the Investigator, subjects with hyperlipidemia may be treated with lipid-lowering agents (e.g., statins) in accordance with standard clinical practice. Doses must be stable in the 2 weeks prior to baseline.

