#### **7.4.2.2 Decrease in eGFR $\leq$ 30% and eGFR $<$ 90 mL/min/1.73 m^2**

During the treatment period, any subject having a  $\leq$ 30% reduction in eGFR to  $<$ 90 mL/min/1.73 m^2 should have the influence of potential contributing factors (as described in [Section 7.4.2.1, Decrease in eGFR  \$>\$ 30% and eGFR  \$<\$ 90 mL/min/1.73 m^2](#)) ruled out and appropriate corrective action taken. Any subject having a  $>$ 20 to  $\leq$ 30% reduction compared to baseline in eGFR to  $<$ 90 mL/min/1.73 m^2 will have a confirmation measurement done within approximately 2 weeks (at a planned study visit, if any, or an unscheduled visit should be completed). The subjects will be managed in the most medically appropriate manner in consultation with the Medical Monitor. The management of the decrease in eGFR may include reduction of dose or temporary interruption.

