## 7.7 Increased Blood Pressure

For all subjects, the target systolic pressure is  $\leq 130$  mmHg and the target diastolic pressure is  $\leq 80$  mmHg. Investigators should use all means possible permitted in the protocol to maintain the BP within these limits. If no further adjustment of antihypertensive therapy is possible, the subject should be discussed with the Medical Monitor.

If on any study day, the mean systolic BP is  $>165$  mmHg or diastolic BP is  $>105$  mmHg and is associated with symptoms of hypertension (i.e., persistent headache, altered mental status, shortness of breath, chest pain consistent with angina pectoris, symptoms of heart failure, evidence of renal insufficiency of new onset, evidence of hypertensive retinal injury (hemorrhages, papilledema)), study treatment should be withheld, an unscheduled visit arranged within 48 hours for repeat BP assessment, the Medical Monitor contacted, and the subject treated as per Investigator local practices and best judgment. The subject will continue with all study visits per the [Schedule of Events](#). Study treatment must not be reintroduced without prior discussion with the Medical Monitor.

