## Appendix 1 Drug Therapy for the Treatment of Hypertension

Antihypertensive drug therapy for subjects who either have hypertension at screening or who develop hypertension while on study treatment may include the following:

- Dihydropyridine calcium channel blockers (e.g., amlodipine, nifedipine)
- Alpha-1-adrenergic blocking agents (e.g., doxazosin)
- Alpha-beta-blockers (e.g., carvedilol, labetalol)
- Thiazide diuretics (e.g., chlorthalidone or hydrochlorothiazide)

Excluded Drugs: While the ARBs and ACE inhibitors may also be effective in calcineurin inhibitor-associated hypertension, their dose adjustment or commencement is not permitted after the screening period (including stabilization visits) in this trial (see [Section 7.6.1, Prohibited Medications](#)).

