### Recommended First and Second Line Therapies for Treatment of Hypertension

Titrate the following according to the timeframe given in the respective drug label:

First Line - select from one of the following:

- Amlodipine, 5 mg daily to achieve BP <140/90 mmHg; titrate to 10 mg daily if satisfactory results not obtained within 2 weeks
- Nifedipine XL, 30 mg daily; titrate to 60 mg and possibly 90 mg daily within 2 weeks
- 12.5 to 25 mg/day of chlorthalidone or hydrochlorothiazide

Second Line - may add from among the following to the first line therapy if a partial response is obtained:

- Labetalol, 100 mg BID; titrate to 200 mg BID, then 300 mg BID

Note: If the BP remains uncontrolled with the above-referenced maximum doses of first and second-line antihypertensive therapies, reduction of study treatment dose may be considered or it may be decided to discontinue study treatment and utilize antihypertensive therapies to achieve control of BP.

**If at any time, in the judgment of the treating physician in consultation with the Medical Monitor, the response to treatment is inadequate, the study treatment may be discontinued.**

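### The note in 7.4.2.1 freezes diuretic doses for the whole study without exception, while Appendix 1 has a thiazide titrated for hypertension, including hypertension that arises on treatment

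*Combined protocol and SAP*

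**What the plan says.** Section 7.4.2.1 deals with eGFR falls of more than 30% from baseline to below 90 mL/min/1.73 m². It interrupts study treatment, asks for a repeat test within 48 hours and names possible contributing factors, dehydration among them. In the same paragraph a note adds that "doses of ACEIs, ARBs, diuretics, and/or lipid lowering therapy are to remain stable throughout the study".

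Appendix 1 gives the drug options for raised blood pressure: "Antihypertensive drug therapy for subjects who either have hypertension at screening or who develop hypertension while on study treatment may include the following". Thiazide diuretics are on that list. The recommended first- and second-line therapies are introduced by "Titrate the following according to the timeframe given in the respective drug label", and one of the three first-line choices is "12.5 to 25 mg/day of chlorthalidone or hydrochlorothiazide". The excluded-drugs paragraph of Appendix 1 rules out adjusting or starting only ARBs and ACE inhibitors after screening.

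Other provisions bear on the same question:

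- Section 7.7 sets an on-study target of 130/80 mmHg or lower and says "Investigators should use all means possible permitted in the protocol to maintain the BP within these limits".
- Section 9.1.3.1 has blood pressure above 130/80 mmHg managed by local practice, with reference to Appendix 1.
- Appendix 5 allows a diuretic to be added for uncontrolled hypertension.
- Inclusion Criterion 5a and Appendix 5 require a stable diuretic dose only for the 2 weeks before baseline.

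**The concern.** A site treating a subject already on a diuretic finds one line that fixes the dose and another that recommends changing it. Two situations matter.

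The first is blood pressure. A subject on 12.5 mg of a thiazide who is above target may go to 25 mg under Appendix 1 but not under the note. Section 7.7 asks for every means that the protocol permits, and whether this one is permitted is what the text leaves open.

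The second is volume. Section 7.4.2.1 names dehydration as a possible reason for a large eGFR fall but gives no corrective step for it. Its only line about diuretics is the freeze. Taken literally, a background diuretic could not be lowered in a volume-depleted subject at the point where lowering it may be the obvious measure.

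**Working it through.** No sample size, error rate or event figure is involved, so the check compares texts.

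1. **Scope of the note (7.4.2.1).** It names diuretics as a class, covers the whole study and gives no exception. Thiazides fall within the word.

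2. **Scope of Appendix 1.** It covers hypertension present at screening or arising on treatment, and so applies during the period that the note covers. The titration instruction stands over the thiazide line. The range is 25 / 12.5 = 2-fold, so titration within it is a dose change.

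3. **Can both be followed?** Not for a subject whose drug is a thiazide and whose dose needs to rise. Both can be followed if the site chooses amlodipine or nifedipine, or adds labetalol.

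4. **When could the need arise?** Entry allows up to 150/90 mmHg at baseline (Inclusion Criterion 5), against an on-study target of 130/80. The differences are 150 − 130 = 20 mmHg systolic and 90 − 80 = 10 mmHg diastolic. A subject may therefore be above target from Day 1. The note does not create this gap, and the gap does not measure the note's effect.

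5. **Which text is the outlier?** Section 7.6.1 names ACE inhibitors and ARBs (for changes in the 2 weeks before baseline) and no diuretic. The Appendix 1 exclusion covers ACE inhibitors and ARBs only. Appendix 6 prohibits on-treatment change for ACEIs and ARBs and has no diuretic row. Appendix 5 has a whole-study stability line for ACEIs, ARBs, aliskiren and unspecified other therapies, but it treats diuretics in a separate entry that carries only the 2-week rule. The note in 7.4.2.1 is the only place that names diuretics in a whole-study freeze.

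6. **Volume depletion.** For falls of 30% or less, Section 7.4.2.2 wants contributing factors "ruled out and appropriate corrective action taken". Section 7.4.2.1 has no matching instruction for larger falls. Section 17.1 bars waivers and allows an unapproved departure only for an immediate hazard or for a logistical or administrative matter. A routine dose change fits neither.

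7. **What is not in conflict.** The 2-week rules before baseline and the permission in Appendix 5 to add a new diuretic do not by themselves contradict a rule on keeping existing doses stable.

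**The case against.** The best answer is that the note means background therapy. Its list (ACEIs, ARBs, diuretics, lipid-lowering drugs) follows Inclusion Criterion 5, 5a and 5b in the same order, and the diuretics there are those for nephrotic edema. On that reading Appendix 1 governs drugs given for blood pressure, and doubt remains only for a thiazide already in use as background therapy. This is the likely intent, and the restriction lists point the same way. It remains an inference, because no section states it. It also leaves the volume problem untouched, since a background edema diuretic is what might need lowering.

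Second, Section 9.1.3.1 and Appendix 1 give written support for a thiazide change made for blood pressure, Appendix 1 is permissive in tone, and other agents are available. That stands. It limits how often the conflict would matter and makes it too strong to say that sites have no cover for such a change.

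Third, the immediate-hazard clause in Section 17.1 could cover a subject with a large eGFR fall, and it would be odd to read 7.4.2.1 as forbidding a correction that 7.4.2.2 requires for smaller falls. Both points are fair. They show that the literal reading is probably unintended, which is a reason to correct the wording.

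A reader might go further and infer that diuretic changes would take subjects out of the per-protocol set. The documents do not support that. Section 17.1 grades deviations case by case, Section 13.3.3 leaves major violations to the SAP, and the per-protocol analysis only confirms the primary result where applicable.

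**Conclusion.** The inconsistency is real and no section resolves it. It is confined to subjects whose drug is a diuretic: those on a thiazide who need a dose change for blood pressure, and those on a background diuretic who become volume-depleted with a fall in eGFR of more than 30%. The conclusion rests on reading the note as written. If it is limited to background therapy, most of the blood-pressure conflict goes and the volume problem stays.

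Its size cannot be given as a number of subjects, because the documents report no entry blood pressures, diuretic use or volume status. The 2-fold dose range and the 20/10 mmHg gap locate the conflict but measure no effect.

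It may be tempting to infer an effect on the remission rate or on the Cohort 2 dose. Nothing in the documents shows one. The Synopsis guidance holds back escalation for eGFR only when at least 5 of the first 5 or 6 subjects have a clinically significant decrease, and it sets aside events obviously unrelated to voclosporin. This is a minor correction to a safety-management rule.

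**What to change.** Amend the note in 7.4.2.1 along these lines:

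> *ACEI, ARB and lipid-lowering doses are held constant for the whole study. Background diuretic doses are also held constant, except for blood-pressure management under Section 9.1.3.1 and Appendices 1 and 5, or for reduction because of volume depletion. The Medical Monitor is to be informed of any such change.*

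A change within the exception then follows the protocol, so no blanket statement about violations is needed.

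Add one listing of subjects with a post-baseline diuretic start or dose change, set beside their eGFR and UPCR course. Section 7.6 already has the dose, dates and reason for each concomitant drug recorded, so no new data are needed. The amendment does not alter the eGFR endpoint: a confirmed fall of more than 30% would still count, and the listing would help a reader interpret it.

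The cost is one amended sentence, one listing and slightly more variation in background diuretic use, which the listing makes visible. The ACEI and ARB freeze, which Appendix 6 ties to the primary endpoint, is unchanged.

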#### **7.4.2.2 Decrease in eGFR $\leq$ 30% and eGFR $<$ 90 mL/min/1.73 m^2**

During the treatment period, any subject having a  $\leq$ 30% reduction in eGFR to  $<$ 90 mL/min/1.73 m^2 should have the influence of potential contributing factors (as described in [Section 7.4.2.1, Decrease in eGFR  \$>\$ 30% and eGFR  \$<\$ 90 mL/min/1.73 m^2](#)) ruled out and appropriate corrective action taken. Any subject having a  $>$ 20 to  $\leq$ 30% reduction compared to baseline in eGFR to  $<$ 90 mL/min/1.73 m^2 will have a confirmation measurement done within approximately 2 weeks (at a planned study visit, if any, or an unscheduled visit should be completed). The subjects will be managed in the most medically appropriate manner in consultation with the Medical Monitor. The management of the decrease in eGFR may include reduction of dose or temporary interruption.

#### **7.4.2.3 Recovery of eGFR**

Subjects experiencing a decrease in eGFR with resultant decrease in dose should be reassessed for recovery of renal function. If the repeated eGFR is  $>$ 80% of baseline, the dose should be increased by 1 capsule BID and eGFR assessed within 2 weeks.

### **7.5 Procedures for Overdose**

Based on clinical experience with voclosporin, symptomatic treatment of AEs or overdoses is indicated. Treatment for renal dysfunction, hypertension, and infection may include dose reduction or dose discontinuation. Magnesium supplementation may be required for hypomagnesemia. Treatment for GI complaints and biochemical/hematological abnormalities, and all other expected AEs, should be based on symptoms, with care taken to rule out other causes.

### **7.6 Prohibited Therapy and Concomitant Treatment**

Any concomitant treatment given for any reason during the course of the study must be recorded in the eCRF and in the subject's source documents, including dosage, start and stop dates, and reason for use.

Any class of medications not mentioned below and with the potential to interfere with evaluation of the study treatment must be discussed and documented with the Medical Monitor.

### 7.6.1 Prohibited Medications

The following medications cannot be taking during the study:

- Cytotoxic or other systemic immunosuppressants
- Initiation of new treatment or change in dosage of ARBs and/or ACE inhibitors within 2 weeks prior to baseline
- Vaccines using live organisms, viral or bacterial
- Current or planned use of ketoconazole or rifampin
- Concomitant use of other CYP3A4/5 inhibitors and inducers should be discussed with the Medical Monitor

[Appendix 6](#) contains a summary of additional treatment and food restrictions.

### 7.6.2 Allowed Concomitant Medications

These medications are permitted during the study:

- Systemic corticosteroids as described in the Inclusion Criteria (see [Section 5.2, Inclusion Criteria](#)) and following the corticosteroid dosing guidelines (see [Section 7.1.2.2, Corticosteroids](#))
- Doses of ACEIs and/or ARBs as described in the Inclusion Criteria (see [Section 5.2, Inclusion Criteria](#))
- Doses of diuretics as described in the Inclusion Criteria (see [Section 5.2, Inclusion Criteria](#))
- Doses of statins as described in the Inclusion Criteria (see [Section 5.2, Inclusion Criteria](#))
- Topical steroids (e.g., nose, scalp, skin, inhaled)
- Herbal supplements can be used with caution and with approval by the Medical Monitor

Treatments which may be used as medically indicated, according to the judgment of the Investigator can be found in [Appendix 5](#). Treatments not included in this list may be acceptable in the study; such treatments should be verified with the Medical Monitor prior to use. A summary of treatment and food restrictions can be found in [Appendix 6](#).

## 7.7 Increased Blood Pressure

For all subjects, the target systolic pressure is  $\leq 130$  mmHg and the target diastolic pressure is  $\leq 80$  mmHg. Investigators should use all means possible permitted in the protocol to maintain the BP within these limits. If no further adjustment of antihypertensive therapy is possible, the subject should be discussed with the Medical Monitor.

If on any study day, the mean systolic BP is  $>165$  mmHg or diastolic BP is  $>105$  mmHg and is associated with symptoms of hypertension (i.e., persistent headache, altered mental status, shortness of breath, chest pain consistent with angina pectoris, symptoms of heart failure, evidence of renal insufficiency of new onset, evidence of hypertensive retinal injury (hemorrhages, papilledema)), study treatment should be withheld, an unscheduled visit arranged within 48 hours for repeat BP assessment, the Medical Monitor contacted, and the subject treated as per Investigator local practices and best judgment. The subject will continue with all study visits per the [Schedule of Events](#). Study treatment must not be reintroduced without prior discussion with the Medical Monitor.

## **8. RISKS/PRECAUTIONS**

No evidence available at the time of the completion of this study protocol indicated that special warnings or precautions are required, other than those noted in the IB [9].

If additional special warnings or precautions become apparent before study completion, Aurinia will notify the Investigator at each site.

## 9. STUDY PROCEDURES

### 9.1 Description of Study Assessments

#### 9.1.1 Laboratory Assessments

Analysis of all samples for hematology, chemistry, hepatic function, lipid profiles, and urinalysis will be performed at a central laboratory using standard validated methods (see the laboratory manual). All study data analyses involving laboratory values will be based on results from the central laboratory.

The UPCr will be calculated both from the first morning void (FMV) and from standard urinalysis results. If the FMV is for some reason not available at Day 1, Week 12 or Week 24, standard urinalysis from a 24-hour urine collection may be substituted as an exception but only after agreement is reached with the Medical Monitor.

Blood and urine samples for the following efficacy and safety assessments ([Table 1](#)) will be drawn in accordance with the [Schedule of Events](#).

**Table 1** Review of Laboratory Assessments

Test Type	Test Parameters	Collection at Visits
Hematology	Complete blood count (CBC) Hematocrit Hemoglobin Mean corpuscular hemoglobin (MCH) Mean corpuscular hemoglobin concentration (MCHC) Mean corpuscular volume (MCV) Platelet count Red blood cells (RBC) Red blood cell morphology White blood cells (WBC)	All
	Differential (absolute and %) Bands Basophils Eosinophils Lymphocytes Monocytes Neutrophils	All

Test Type	Test Parameters	Collection at Visits
Coagulation	Coagulation Activated partial thromboplastin time (aPTT) Prothrombin time (PT) Partial thromboplastin time (PTT)	Screening
Blood Chemistry	Alanine aminotransferase (ALT) Albumin Alkaline phosphatase (ALP) Aspartate aminotransferase (AST) Bicarbonate Bilirubin (direct and total) Blood urea nitrogen (BUN) Calcium Chloride	All
	Cholesterol (total, HDL, and LDL) & triglycerides Creatine kinase	Day 1 and Week 24
	Creatinine Gamma-glutamyl transferase (GGT) Glucose	All
	Glycosylated hemoglobin (HbA1c)	Day 1 and Week 24
	Lactic dehydrogenase (LDH) Magnesium	All
	Phosphorous, inorganic	Day 1 and Week 24
	Potassium Protein, total Sodium	All
	Urinalysis and urine microscopy	Complete urinalysis (to include urine protein, creatinine, blood, urine microscopy).
FMV urine collection	FMV will be performed to analyze UPCR.	All
24-hour urine	UPCR	Day 1, Week 12 and Week 24 Note that 24-hour urine collection should be scheduled so as not to coincide with the FMV sampling due on the day of the study visit

Test Type	Test Parameters	Collection at Visits
Pregnancy Test	For females of childbearing potential.	Serum pregnancy test to be evaluated at central laboratory at Screening, and Week 24; urine pregnancy test will be performed locally at all other applicable visits.
Serology	Cytomegalovirus Hepatitis A, B, and C Hepatitis B surface antigen (HBsAg)	Screening (including stability assessments)
Special Tests	Estimated glomerular filtration rate (eGFR)	All
Biomarkers	Urine nephrin Urine synaptopodin Serum TGF- $\beta$	Day 1, Week 4 and Week 24

Notes: FMV = First morning void; HDL = High-density lipoprotein; LDL = Low-density lipoprotein; UPCR = Urine protein creatinine ratio.

The total amount of blood that will be collected during the study from an individual subject is approximately 200 mL over 34 weeks.

For details on whether laboratory abnormalities should be reported as AEs and on the follow-up required in such cases, see [Section 10.2.4, Clinical Laboratory Evaluations](#).

